**Organization**

At the Surgical Centre for Movement Disorders at Vancouver General Hospital, we have a 15-year experience with DBS surgery and programming for movement disorders. Patients eligible for this study will be all patients who have already underwent or who will be undergoing thalamic DBS surgery to ameliorate their essential tremor. Patients will be tracked through [name] clinic and given a research identification number. After enrollment, they will be followed-up by [name] and programming will begin one-month after surgery. Data will be burned onto a CD using only their research identification number. This data will then be analyzed to determine if there is an improvement in the patient’s spasmodic dysphonia symptoms and quality of life. The results will be published in a peer-reviewed journal with no reference to individual patients.

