## ***Clinical Motivation***

Our team recently studied a small cohort of patients with LD and concurrent ET who underwent DBS for their ET. We found that these patients tremendously improved in their voice as a result of DBS. Scattered case reports are present in the literature of thalamic DBS improving voice in LD and concurrent ET. Based on our recent study and others elucidating the neural circuitry of LD, we are hoping to initiate a Phase 1 DBS trial in pure LD patients (those without essential tremor). This trial will be of international significance, span multiple specialties, and potentially revolutionize the standard of care for these patients.

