## **Hypothesis**

The ventral intermediate nucleus (Vim) of the motor thalamus receives somatosensory input from the cerebello-thalamic circuit (1-2,9). This circuit is desynchronized in LD as previous studies have shown that the Vim is involved in the motor control of laryngeal musculature (1,9). We believe that neuromodulation of this cerebellar circuit at the Vim will lead to significant vocal improvement in LD patients. We recently targeted the Vim for patients with coincident essential tremor and LD. We found that patients significantly improved in voice,

neurological, and quality of life outcomes; this publication is currently under preparation.

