### Study Design

To investigate our hypothesis, we will conduct a prospective, randomized, double-blinded, crossover Phase 1 DBS trial in LD patients. Patients will be randomized to either active or sham-stimulation for 3 months, crossed-over, and conclude with open-label treatment for 6 months. Patient and assessors will be blinded to treatment allocation. Below is a graphical illustration of trial.

Previous Phase 1 trials for new indications of DBS have recruited N=6 patients. We plan to also recruit N=6 patients for this trial from the Pacific Voice Clinic. We will use a computer-generated 1:1 pairwised randomization sequence when the patients are enrolled into the trial, so that similar numbers of patients are recruited to each study group. Patients will be evaluated in a double-blinded manner for their voice and voice-related quality of life. Patients and rating clinicians will be masked to treatment allocation; an unmasked clinician will be responsible for programming the stimulation.

DBS stimulation parameters will be chosen based on standard programming guidelines. Primary endpoints will assess: (1) patient improvement in SD using the Unified Spasmodic Dysphonia Rating Scale (2) assess patient quality of life using the Voice-Related Quality of Life. Patients will also be asked their subjective assessment of each of the settings. [name] will be administering these scales.

We also will acquire two advanced neuroimaging scans: PET and DTI. The former will allow us to monitor neural network wide changes as a result of DBS. DTI will allow us to determine which white matter tracts are being activated as a result of this surgery. Once pilot\* testing of the PET protocol is completed, patients enrolled in this trial will be asked to obtain a PET scan at end of the 3-month mark and at the 6-month mark (see trial timeline above). DTI scan will only be required pre-operatively. The neuroimaging arm of our surgical trial will add considerable scientific rigour to our trial and helps us further elucidating the neurobiology of this disease.

At the Vancouver General Hospital (VGH), we have a 17-year experience with Deep Brain Stimulation Surgery. As of 2012, we have performed over 400 of these operations including DBS stimulator programming.

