### **Significance**

The significance of this research is two-fold: improving the patients’ spasmodic dysphonia symptoms and secondly, providing neurosurgeons with a strategy of treating spasmodic dysphonia. This trial will be of international significance as it is the first time these dystonia patients will be undergoing DBS intervention.

In the past, otolaryngologists have been involved in treating spasmodic dysphonia cases. Our study has the potential to show that perhaps, DBS can be used for pure spasmodic dysphonia as well. This will be the largest study reported in the literature on studying the effects of DBS on spasmodic dysphonia. Based on the limitations of existing treatments, DBS can provide SD patients with a long-term and sustained relief from their voice disorder. Our work has the potential to revolutionize the care provided for these patients.

SD is the third most common focal dystonia followed by cervical dystonia and blepharospasm. This disorder has classically been thought of as a disorder of the laryngeal muscles or of psychogenic origins. Recent neuroimaging studies have emerged indicating the presence of a central neurological abnormality in the basal ganglia of SD patients (6). Thus, our current investigations are aimed at determining the efficacy of DBS for SD.

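### The only eligibility sentence requires surgery for essential tremor, but the trial is set in patients without essential tremor

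*Combined protocol and SAP*

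**What the plan says.** The Clinical Motivation section describes the planned study as a "Phase 1 DBS trial in pure LD patients (those without essential tremor"). It separates this from earlier work: "Our team recently studied a small cohort of patients with LD and concurrent ET who underwent DBS for their ET". The Hypothesis section refers to the same kind of patient: "We recently targeted the Vim for patients with coincident essential tremor and LD".

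The Organization section then says that the patients eligible for this study are "all patients who have already underwent or who will be undergoing thalamic DBS surgery to ameliorate their essential tremor". In the text available, no other sentence states who is eligible.

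Two further sections touch on the population. Study Design speaks of LD patients without mentioning ET and gives the source and size: "We plan to also recruit N=6 patients for this trial from the Pacific Voice Clinic". Significance says the work may show that "DBS can be used for pure spasmodic dysphonia as well", without defining the pure form.

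Two timing statements also bear on the point. Study Design says "DTI scan will only be required pre-operatively", and Organization says that after enrolment "programming will begin one-month after surgery".

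**The concern.** The rule that admits patients and the statement of what the trial is for describe different people. If sites follow the eligibility sentence, the trial enrols patients operated on for ET, who resemble the group the team says it has already studied, and it cannot address LD without ET. If they follow the stated aim, the question can be addressed, but every patient enrolled departs from the written eligibility sentence.

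The sentence also admits patients who have already had surgery. The plan does not say how the pre-operative scan, or a programming start counted from surgery, would apply to them. Nor does it say what baseline means for them, although the repeated measures ANOVA in the Statistics section compares baseline with the on- and off-stimulation periods.

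**Working it through.** There is no planned figure to reproduce. Study Design justifies N=6 by precedent only, with no effect size, standard deviation or power. The check compares text and adds simple counts.

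**Inputs**

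| Source | Population or fact | ET status |
|---|---|---|
| Clinical Motivation (aim) | Pure LD | Excluded |
| Organization (eligibility) | Past or planned thalamic DBS for ET; LD not named in the sentence | Required |
| Study Design | LD patients from a voice clinic, N=6 | Not mentioned |
| Significance | Pure spasmodic dysphonia, undefined; DBS described as a first for these patients | Not mentioned |
| Clinical Motivation and Hypothesis (earlier work) | LD with ET, treated with DBS | Present |
| Details of PET Study | At least 1 trial participant already recruited | Not given |

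**Step 1: overlap.** Let A be the population in the aim (LD and no ET) and B the population in the eligibility sentence (thalamic DBS done or planned to treat the patient's own ET). Every member of B has ET and no member of A does, so the overlap of A and B is 0 patients.

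**Step 2: consequence for the six patients.**
- Eligibility sentence applied: all 6 are in B, so 0 of 6 are in A.
- Aim applied: all 6 are in A, so 0 of 6 are in B, and 6 − 0 = 6 of 6 deviate from the eligibility sentence.

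These counts restate the contradiction at the planned sample size. They do not measure actual enrolment.

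**Step 3: does another section settle it?** Study Design and Significance fit the aim better than the eligibility sentence, but neither excludes ET. Only Clinical Motivation does that. The eligibility sentence is worded for this study and in the future tense, so it cannot be read as a description of the earlier cohort. It resembles that cohort in being tied to DBS for ET, but the match is partial. The cohort also had LD, which the sentence does not name. Read literally, it would admit an ET patient without LD, although the same section later refers to spasmodic dysphonia symptoms.

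**Step 4: patients already implanted.** A scan required before surgery and programming that starts one month after surgery, following enrolment, both assume that surgery comes after entry. The description in Significance of DBS as a first for these patients points the same way. This is a tension with admitting patients already operated on, not a strict contradiction, because the text does not say how these steps would apply to them.

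**The case against.** The strongest reply is that the sentence is a leftover in an administrative section and that the rest of the plan makes the intention clear. Organization mostly covers tracking, identification numbers and data storage. Clinical Motivation, Study Design, Significance and Novelty all present DBS as a treatment for LD. There is a small sign that sections were written at different times: Study Design gives 17 years of DBS experience, while Organization gives 15. On this view, six patients operated on for ET would be unlikely to be enrolled in practice.

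Part of this stands. Carry-over is plausible, but the documents do not confirm it, and the difference in years is only circumstantial. A leftover sentence that defines the wrong population still has to be corrected, because it is the only one that says who is eligible. Treating Clinical Motivation as soft background does not help either, since the pure-LD aim would then have no criterion behind it.

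A second reply is that a sample with both LD and ET would not be worthless. The Hypothesis section speaks of LD patients generally, so such a sample could bear on it. That also stands. What it could not support is a conclusion about LD without ET.

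Finally, some pages and the trial figure are not in the text available, so other criteria may exist elsewhere. The two statements would still conflict.

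**Conclusion.** The concern holds and must be fixed. The eligibility sentence and the stated aim define populations with zero overlap: 0 of 6 patients would be in the target population under one rule, and 6 of 6 would deviate under the other. This rests on the literal wording of both sentences, on taking surgery for a patient's ET to mean that the patient has ET, and on N=6. No effect size or power is involved. Confidence is high for the contradiction itself. That no other eligibility criteria exist can be said only of the text available. The point about previously implanted patients is secondary. At least 1 participant had already been recruited when the PET section was written. The documents do not give that patient's ET status, so no actual deviation is shown.

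**What to change.** Replace the two statements with one eligibility statement that matches the objective, and bring Clinical Motivation, Study Design, Significance and Organization into line with it. The choice of population is the sponsor's. The statement should:

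- say explicitly whether LD is required and whether ET is required, allowed or excluded;
- say whether previously implanted patients may enter and, if so, how the pre-operative DTI scan, the one-month programming start and the baseline assessment apply to them.

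If patients with ET are intended, restate the objective and limit the conclusions to that population. Check every participant already recruited against the reconciled statement and record the result.

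The expected cost is a short protocol amendment plus that check. This assumes that those already recruited meet the reconciled criteria. If any do not, the cost would be larger.

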### **Adverse Events**

There can be temporary side effects related to the stimulation spreading outside the target area of the brain. These side effects depend on what area of the brain is being stimulated and can include tingling, muscle tightness, double vision, hoarse speech, and dyskinesia. These temporary side effects can be adjusted and resolved by the DBS Clinicians and be minimized. In this study, if any adverse events occur, the patient will be able to contact [name] on a 24/7 basis. The DTI scan is a standard MRI scan and carries no additional risk to the patient. The PET scan will use ligands that expose the patient to radiation. Each PET scan entails a radiation exposure similar to a single transatlantic 6-hour flight.

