**Statistics**

We will compare the primary (Unified Spasmodic Dysphonia Rating Scale) and secondary endpoints (Quality of Life) at baseline, for the off- stimulation period and the on-stimulation period, with repeated measures ANOVA. For the endpoints in which a significant effect of timepoint ( $p < 0.05$ ) was identified, pairwise comparisons will be performed between each of the three timepoints (baseline *versus* off stimulation, baseline *versus* on stimulation, and on stimulation *versus* off stimulation) and a Bonferroni-corrected p values will be completed.

We will also compare the effect of randomisation sequence on the difference in USDRS scores between the on-stimulation and off-stimulation periods in the blinded phase of the trial using an unpaired *t* test.

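### Eligibility extends to patients already implanted with thalamic DBS, which conflicts with the DTI and programming timing and leaves the baseline contrasts undefined and possibly biased

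*Combined protocol and SAP*

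**What the plan says.** The only explicit eligibility sentence in the readable text is in Organization. It admits "all patients who have already underwent or who will be undergoing thalamic DBS surgery", and goes on to give relief of essential tremor as the purpose of that surgery. The same section says that, after enrolment, "programming will begin one-month after surgery".

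Other sections describe a patient who has not yet been implanted:

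- Study Design: "DTI scan will only be required pre-operatively".
- Significance: "it is the first time these dystonia patients will be undergoing DBS intervention".
- Clinical Motivation: the trial is to be in "pure LD patients (those without essential tremor"), which also disagrees with the diagnosis named in Organization.

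The Statistics section compares baseline, the off-stimulation period and the on-stimulation period by repeated measures ANOVA. If the timepoint effect has p < 0.05, "pairwise comparisons will be performed between each of the three timepoints", with Bonferroni correction. Study Design sets N = 6, 3 months on each of active and sham in a crossover, and states: "Patients and rating clinicians will be masked to treatment allocation".

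**The concern.** The eligibility rule creates two kinds of patient, and the rest of the plan is written for one of them. Someone implanted before enrolment cannot supply a pre-operative scan at enrolment. That person could meet the programming start only if enrolled within about a month of surgery.

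The statistical consequence runs through baseline. In a patient not yet stimulated, baseline is an untreated state. In a patient enrolled with the device running, baseline may already carry some or all of the treatment effect. Averaging the two mixes different quantities in baseline versus on and baseline versus off. With 6 patients, one such patient is 17% of the data.

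The possibility is not remote. Clinical Motivation and Hypothesis describe the team's own recent patients with laryngeal dystonia and essential tremor, who had DBS and whose voice improved. The Organization wording would admit them.

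**Working it through.** **Text comparison**

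| Element | Section | Can an already-implanted patient meet it? |
|---|---|---|
| DTI before the operation only | Study Design | Not if enrolled after surgery |
| Programming after enrolment, one month after surgery | Organization | Only if enrolled within about a month of surgery |
| First DBS for these patients | Significance | No |
| Baseline as an analysis level | Statistics | Undetermined: timing and stimulation state not given |
| Masking of patients and raters | Study Design | Not excluded by the text |

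**Size of a possible baseline shift**

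The plan gives no effect size, standard deviation or power for N = 6, so there is no figure of its own to reproduce.

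Inputs: n = 6 (Study Design) and three levels, two of whose three pairwise contrasts use baseline (Statistics). Assumptions: D is the true improvement on versus off; k is the number entering with stimulation running; f is the share of D present at their baseline. Carry-over, period effects and any lasting effect of the implant itself are taken as absent.

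- Not yet stimulated (6 − k patients): baseline to on = D; baseline to off = 0.
- Already stimulated (k patients): baseline to on = D − fD; baseline to off = −fD.
- Mean baseline to on = [(6 − k)D + k(1 − f)D]/6 = D(1 − fk/6).
- Mean baseline to off = −fDk/6.
- Mean on versus off = D for any k and f.

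| k | Baseline to on, f = 1 | Spurious worsening, baseline to off, f = 1 | Baseline to on, f = 0.5 | Spurious worsening, f = 0.5 |
|---|---|---|---|---|
| 0 | 1.00D | 0 | 1.00D | 0 |
| 1 | 0.83D | 0.17D | 0.92D | 0.08D |
| 2 | 0.67D | 0.33D | 0.83D | 0.17D |
| 3 | 0.50D | 0.50D | 0.75D | 0.25D |
| 6 | 0 | 1.00D | 0.50D | 0.50D |

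With f = 0 (stimulation fully washed out at baseline) there is no shift for any k.

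**Effect on the tests**

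The Statistics plan was simulated: one-way repeated measures ANOVA at 0.05, then paired t tests at 0.05/3 = 0.0167. There were 40,000 runs with f = 1, independent visit errors of SD 1, and D = 2 of those SDs (assumed). The table gives the proportion significant.

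| k | ANOVA gate | Baseline vs on | On vs off, after gate | On vs off, no gate |
|---|---|---|---|---|
| 0 | 0.87 | 0.53 | 0.53 | 0.54 |
| 1 | 0.74 | 0.26 | 0.50 | 0.54 |
| 2 | 0.63 | 0.12 | 0.47 | 0.54 |
| 3 | 0.60 | 0.05 | 0.45 | 0.53 |

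From k = 0 to k = 3, power for baseline versus on falls from 0.29 to 0.04 at D = 1.5, and from 0.89 to 0.06 at D = 3. On versus off loses power only because the gate contains baseline; without the gate it does not change with k beyond simulation error.

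**The case against.** The strongest reply is that k may well be 0. The sentence concerns essential tremor patients, whereas Clinical Motivation specifies patients without tremor, Significance calls this a first DBS intervention, and Study Design recruits from a voice clinic. The sentence may have been carried over from work on the earlier tremor cohort. That is plausible, and the tremor conflict is the more basic one. But correcting only the diagnosis would leave surgery already performed within the rule, so the point survives that correction.

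Three stronger readings are tempting, and the documents do not support them:

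- *The baseline contrasts are wrong.* The readable text does not fix when baseline is taken or whether stimulation is on. Study Design refers to a trial diagram that is not shown and may define this, or may show a period without stimulation. So it cannot be said that baseline must precede implantation, or that no washout is planned. The contrasts are undefined and possibly biased.
- *Masking requires enrolment before implantation.* It does not. In a crossover, any patient who receives active first also knows stimulation before sham. Earlier exposure could add to recognition of sham, but nothing in the documents allows this to be quantified.
- *The main treatment comparison is biased through baseline.* The randomised on-versus-off estimate does not use baseline. Only its test is affected, through the gate.

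The DTI safety sentence in Adverse Events ("The DTI scan is a standard MRI scan and carries no additional risk to the patient") does not mention implant status, and no weight is placed on it. DTI also plays no part in the Statistics section, so a missing scan is a loss to the imaging aim and not to the endpoint analysis.

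**Conclusion.** The concern holds as an internal contradiction with a conditional statistical consequence. The eligibility rule, followed as written, admits patients who cannot meet the DTI timing and, in most cases, the programming timing, and it conflicts with the description of a first DBS intervention. This is a faulty stated rule, not merely missing detail.

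The bias in the two baseline contrasts is f×D×k/6. The figures of 17%, 33% and 50% of D for k = 1, 2 and 3 are a worst case that assumes full voice benefit at baseline. They halve at f = 0.5 and vanish at f = 0 or k = 0. The documents give neither k nor f, so the range is from nothing to the whole of D. On versus off keeps its estimate. Under the simulation's assumptions (D = 2 visit SDs, f = 1), its power after the gate falls from 0.53 to 0.45 at k = 3.

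This should be corrected before enrolment: the rule touches two of three planned comparisons, and the correction is a matter of wording.

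**What to change.** 1. In Organization, remove the part of the eligibility sentence that covers surgery already performed, and state that only patients without previous DBS are eligible. Resolve the essential tremor wording in the same sentence, so that it agrees with Clinical Motivation, Study Design and Significance. Removing the first part alone would leave the tremor conflict in place.
2. In Statistics, state that baseline USDRS and voice-related quality of life are measured before any stimulation. In Study Design, state that DTI is completed before implantation. A baseline after surgery but before programming would still be stimulation-naive, so the text should say which is meant.
3. If an already-implanted patient is kept, leave that patient out of both baseline contrasts and out of the three-level ANOVA. Test on versus off directly, without the gate that contains baseline, and report it with and without that patient.

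The cost is protocol wording and a slightly smaller recruitment pool. Study Design already plans to recruit all six from a voice clinic, so the loss should be small.
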